4 MATERIALS AND METHODS

4.1 STUDY DESIGN

4.1.1 OVERALL DESIGN

This study is a prospective, double-masked (investigator and participant), bilateral, randomized, cross-over dispensing study comparing the MD-T test lens against the 1-DAM-T and DACP-T control lenses. Each participant will be randomized to wear either the test or one of the controls with similar/comparable lens parameters optimized for vision. Both test and control lenses will be

used in their approved daily disposable lens wear modality for one (1) week. It is anticipated that this study will involve up to 4 scheduled visits:

Visit 1: Baseline includes screening and dispense of lens pair #1,

Visit 2: 1-week follow-up visit of lens pair #1 and dispense of lens pair #2,

Visit 3: 1-week follow-up visit of lens pair #2 and dispense of lens pair #3,

Visit 4: 1-week follow-up visit of lens pair #3 and study exit.

The study design is shown in Figure 1.

[figure not shown]

Figure 1: Study Design

4.1.2 RANDOMIZATION

A randomization schedule will be generated using a web-based program:

(www.randomization.com). An example of the format generated is given in Appendix 24. The final study randomization schedule will be generated by the CCLR Data Management Team, and provided to the research assistants for use during the study. Study investigators will remain masked to the randomization schedule until the study is completed and the database is locked.

4.1.3 MASKING

Participants will be masked as to lens type and lens assignment (control lenses vs. test lens). Lenses dispensed to participants may be either over-labelled or have part of the label obscured, however the safety information on the outer package label of the contact lens, shall be clearly visible. Investigators will be masked as much as possible however it may not be possible to fully mask the investigators, because identifying lens markings may be visible during the biomicroscopy examination.

4.2 STATEMENT OF COMPLIANCE

This protocol document has been developed in accordance with the following:

- ISO 14155 Clinical Investigation of Medical Devices for Human Subjects, Parts 1 & 2
- ICH Harmonized Tripartite Guideline for Good Clinical Practice
- The University of Waterloo's Guidelines for Research with Human Participants
- Tri-Council Policy Statement: Ethical Conduct for Research Involving Humans, 2nd Edition. <http://www.pre.ethics.gc.ca/eng/policy-politique/initiatives/tcps2-eptc2/Default/>
- Declaration of Helsinki

4.3 ETHICS REVIEW

This study will be conducted in accordance with Institutional Review Board regulations (U.S. 21CFR Part 56.103) or applicable IEC regulations. Copies of all IRB/IEC correspondence with the investigator/sponsor will be kept on file.

This protocol will be submitted to and reviewed through the Office of Research Ethics (ORE) at the University of Waterloo, Canada. Notification of ethics clearance of the application is required prior to the commencement of the study. The conduct of this study will be given clearance by the Clinical Research Ethics Committee at the University of Waterloo, Canada.

4.4 CLINICAL TRIAL REGISTRATION

This study will be registered in the clinical trials registry (<https://clinicaltrials.gov/>) by the study sponsor.

4.5 INFORMED CONSENT

Informed consent shall be obtained in writing from all participants prior to their enrolment in the study (Appendix 1), and before any procedure specific to the clinical investigation is carried out.

4.6 STUDY POPULATION

4.6.1 NUMBER OF PARTICIPANTS

Up to 52 participants will be dispensed / randomized with study products, with a target of 45 completing the study. Participants will be recruited using CCLR records and advertising approved by the UW Office of Research Ethics (Appendices 2, 3a, and 3b). Each participant will be given a unique ID number. Additionally, all participants must meet the study inclusion and none of the exclusion criteria listed below.

4.6.2 INCLUSION AND EXCLUSION CRITERIA

A person is eligible for inclusion in the study if he/she:

1. Is at least 17 years of age and has full legal capacity to volunteer;
2. Has had a self-reported oculo-visual examination in the last two years.
3. Has read and signed an information consent letter;
4. Is willing and able to follow instructions and maintain the appointment schedule;
5. Is an adapted soft contact lens wearer;
6. Is willing to wear contact lens in both eyes for the duration of the study;
7. Has a minimum spectacle astigmatism of - 0.75;
8. Can be fit with the three study contact lens types in the powers available;
9. Has a visual acuity of 20/30 or better in each eye with habitual correction, or 20/20 best corrected vision (for binocular distance acuity);
10. Can achieve a distance visual acuity of 20/30 (0.18 logMar) or better in each eye with the study contact lenses.
11. Has clear corneas and no active* ocular disease;

A person will be excluded from the study if he/she:

1. Is participating in any concurrent clinical trial;
2. Has any known active* ocular disease and/or infection;
3. Has a systemic condition that in the opinion of the investigator may affect a study outcome variable;
4. Is using any systemic or topical medications that in the opinion of the investigator may affect a study outcome variable;
5. Has known sensitivity to fluorescein dye or products to be used in the study;
6. Appears to have any active* ocular pathology, ocular anomaly or severe insufficiency of lacrimal secretion (severe dry eye) that would affect the wearing of contact lenses;
7. Is pregnant, lactating or planning a pregnancy at the time of enrolment (by verbal confirmation at the screening visit);
8. Is aphakic;
9. Has undergone refractive error surgery.

* For the purposes of this study, active ocular disease is defined as infection or inflammation which requires therapeutic treatment. Mild (i.e. not considered clinically relevant) lid

abnormalities (blepharitis, meibomian gland dysfunction, papillae), corneal and conjunctival staining and dry eye are not considered active ocular disease. Neovascularization and corneal scars are the result of previous hypoxia, infection or inflammation and are therefore not active.

4.6.3 REPEATED SCREENINGS

In some circumstances a repeated screening may need to be scheduled. Examples include, but are not limited to:

1. Incomplete information available at time of screening to determine eligibility (e.g. current lens brands worn, history from current eye care practitioner etc.)
2. Study procedures unable to be completed in time scheduled for visit;
3. Study products not available at the time of the screening visit;
4. A transient health condition which may affect the eye(s) (e.g. a common cold, active allergies, fatigue etc.)
5. The short term use of medications (e.g. antibiotics, antihistamines etc.)
6. Reassessment of baseline ocular conditions (e.g. corneal and/or conjunctival staining, scars etc.)

The maximum total number of screenings permitted will be 3.

4.7 STUDY MATERIALS

4.7.1 LENSES

Details of study lenses are show in Table 1.

Table 1: Lens parameters to be used in this study

	MyDay Toric	1-DAY ACUVUE MOIST for ASTIGMATISM	DAILIES AquaComfort Plus Toric
Manufacturer	CooperVision Inc.	Johnson & Johnson Vision Care	Alcon Canada Inc.
Material	stenfilcon A	etafilcon A	nelfilcon A
Health Canada license #	91502	2519	92503
EWC (%)	54%	58%	69%
Dk/t (-3.00D)	100.0	23.7	26
BOZR (mm)	8.4	8.5	8.80
Diameter (mm)	14.2	14.5	14.4

	MyDay Toric	1-DAY ACUVUE MOIST for ASTIGMATISM	DAILIES AquaComfort Plus Toric
Sphere power (D)	0.00 to -6.00 (0.25 steps) -6.50 to -8.00 (0.50 steps)	0.00 to -6.00 (0.25) -6.50 to -8.00 (0.50)	0.00 D to -6.00 (0.25) -6.50 to -8.00 (0.50)
Cylindrical Power (D)	-0.75, 1.25, -1.75	-0.75, 1.25, -1.75	-0.75, 1.25, -1.75
Axis (degree)	10°, 90°, 170°, 180°	10°, 90°, 170°, 180°	10°, 90°, 170°, 180°

4.7.2 CONTACT LENS CARE SYSTEM

No contact lens care system is required for this study as all lenses are daily disposable lenses to be worn for a single day only and then discarded. New lenses will be worn each day.

Lenses worn for the scheduled visits at the 1 week follow-up visit will be collected by and stored in saline.

4.7.3 REWETTING DROPS

Participants will not be encouraged to use rewetting drops; however, those who habitually used rewetting drops will be allowed to continue using their normal drops. Rewetting drop use will be recorded at each visit. In the event of an adverse event, rewetting drops may be given to participants.

4.7.4 CONTACT LENS DISPENSING

The lenses will be provided to the participant after being transferred, complete with blister pack solution, to a contact lens cup; this will maintain participant masking and aid investigator masking. The use of saline for rinsing the contact lens prior to insertion is permitted if necessary. Saline will not be dispensed during the study.

4.7.5 ORDERING CONSUMABLES

The MyDay Toric study lenses will be provided by the Sponsor. The control lenses will be purchased by the CCLR for use in the study.

The investigator must maintain an accurate accounting of the study product during the study. A detailed inventory must be completed for study supplies.

4.7.6 DISPOSING OF CONSUMABLES

This study provides consumables (lenses) to participants for use during the study. Participants will be instructed to dispose of worn lenses (both test and control lenses) daily, but retain the

foils of all used lens packs and return them together with any unworn lenses, at their next study visit. Lenses worn for the scheduled visits will be collected from the participants and they will be disposed according to UW guidelines. Worn lenses associated with adverse events may be retained either at the CCLR or returned to CooperVision. Typical analysis in these cases relates to inspection for damage and/ or bacterial contamination. Upon completion of the study, all lenses (both used and unused) will be destroyed, unless otherwise directed by the study Sponsor.

4.7.7 PRODUCT ACCOUNTABILITY

Accountability logs will be kept to include the number of lenses received, dispensed, unused, and returned to vendor (where relevant). All products dispensed to participants will be recorded in the participant's accountability log.

4.8 SCHEDULED AND UNSCHEDULED VISITS

This study has a total of 4 scheduled study visits, including:

- Visit 1: Baseline includes screening and dispense of lens pair #1,
- Visit 2: 1-week follow-up visit of lens pair #1 after 7-10 days and dispense of lens pair #2;
- Visit 3: 1-week follow-up visit of lens pair #2 after 7-10 days and dispense of lens pair #3;
- Visit 4: 1-week follow-up visit of lens pair #3 after 7-10 days and study exit.

A scheduled follow-up visit may only take place when the participant attends wearing the study lenses. If this is not the case and the participant is not experiencing any problems with the lenses, the appointment will be rescheduled, ideally within the visit window.

Visits that fall outside of the specified visit windows will be designated as protocol deviations and at the end of the study the data collected will be assessed for its suitability to be included in the analysis population.

4.8.1 STUDY VISITS

The summary of visit codes is shown in Table 2.

Table 2: Summary of visit codes

Visit #	Visit code	Visits
Visit 1	V1 (V1-R1, & V1-R2 for re-screening if applicable)	Screening,
	V1-1	Baseline & dispensing lens pair #1

Visit 2	V2	1-week follow-up of pair #1 (day 7 -10 from dispense of pair #1) & dispensing pair #2
Visit 3	V3	1-week follow-up of pair #2 (day 7 -10 from dispense of pair #2) & dispensing pair #3
Visit 4	V4	1-week follow-up of pair #3 (day 7 -10 from dispense of pair #3) & Study exit

4.8.2 SCREENING

All participants who sign the informed consent letter will be assigned a study ID number. The investigator will determine participant eligibility using the inclusion and exclusion criteria. Ineligible participants will be discontinued from the study. The procedures to be performed are outlined below:

- The participant is expected to attend the screening / baseline visit not wearing their habitual contact lens products.
- The participant will be required to read and sign an Informed Consent Form prior to enrollment. When the participant has signed the consent form, the participant will be considered to be enrolled in to the study.
- Participant demographics and medical history (age, sex, medical conditions, medications, allergies)
- Contact lens history (own lens information, and wear time)
- Baseline visual acuity with spectacles or spectacle refraction.
- Auto refraction/auto keratometry: Horizontal and Vertical K readings (D)
- Sphero-cylindrical refraction (D), monocular & binocular distance visual acuity (high contrast) (logMAR)
- Palpebral aperture size
- HVID measurements
- Slit lamp biomicroscopy will be assessed according to the approved study biomicroscopy CRF (Appendix 9).
- The investigator will confirm that the participant meets the eligibility specifications set out in the inclusion criteria and exclusion criteria and is eligible to continue in the study.
- Trial fitting of all three study lenses will be done:
 - The contact lens power will be chosen based on the vertexed spectacle refraction. For each eye, the test and control lenses will be optimized for vision, with similar/comparable lens parameters.

- The contact lenses will be provided to participants in a manner which does not unmask the participant, as described in Section 4.7.4.
- The lenses will be inserted by the participant.
- Monocular over refraction will be done to determine if a different power is needed. If any changes are made, the above procedures will be repeated.
- Monocular and binocular logMAR visual acuity will be recorded with high contrast letters under high room illumination (300-600 lux), and the final lens power will be recorded.

4.8.3 DISPENSING LENS PAIR #1

The participant will be assigned a randomization ID and the first pair (lens pair #1) of contact lenses (either test or one of the control lenses) will be selected according to the randomization table.

- Lens pair #1 will be provided to participants in a manner which does not unmask the participant, as described in Section 4.7.4.
- The lenses will be inserted by the participant.
- The contact lenses will be allowed to settle for 10 minutes.
- The participant will be asked to give subjective binocular ratings for:
 - Comfort at insertion (0-10 scale)
 - Ease of insertion (0-10 scale)
 - Speed of settling (0-10 scale)
 - Visual quality (0-10 scale)
 - Vision stability (0-10 scale)
 - Overall satisfaction (0-10 scale)
- Monocular and binocular logMAR visual acuity will be recorded with high contrast letters under high (300-600 lux) and low (1-5 lux) room illumination.
- Lens surface and fit will then be assessed and graded according to the CVI grading scales for the following:
 - Lens wettability (0-4 scale)
 - Centration (mm)
 - Post-blink movement (mm)
 - Toric mark visibility

- Lens orientation (3 measurements per lens)
 - Overall stability of toric mark position
 - Overall lens fit acceptance (0-4 scale)
- The participant will be given a set of daily subjective questionnaires (Appendix 12) to be completed at home on days 1, 3 and 6 starting the morning after the dispensing visit (day 0), to reflect their lens wear experience at the time of rating. Participant will be given careful explanation of how and when to complete them. Questions will include:
 - Time of lens insertion and removal
 - Comfort after insertion (i.e. after lens settling), after 4, 8, and 12 hours, and just before lens removal (0-10 scale)
 - Dryness after 4, 8, and 12 hours, and just before lens removal (0-10 scale)
 - Visual quality/clarity after insertion (i.e. after lens settling), after 4, 8, and 12 hours, and just before lens removal (0-10 scale)
 - Vision stability after insertion (i.e. after lens settling), after 4, 8, and 12 hours, and just before lens removal (0-10 scale)

The participant will be asked to wear the study lenses for at least 12 hours per day and 6 days per week.

- Participant will be provided with sufficient contact lens supply.
- The participant will be discharged and reminded to return for the 1-week visit of lens pair #1 and to bring back all lens package foils.

4.8.4 1-WEEK FOLLOW-UP OF PAIR #1 & DISPENSING PAIR #2

Participants will be asked to wear lenses for at least 4 hours prior to the visit appointment. Participants who attend without lenses in-situ (wearing lenses) for at least four hours will be rescheduled.

- The participant will be asked to score their subjective responses by reflecting on a typical day during the previous week of lens wear, as detailed in the subjective ratings form (Appendix 11) and includes the following:
 - Wear time at this visit (hours)
 - Wear time per day during previous 1 week (hours)
 - Comfortable wear time per day during previous 1 week (hours)
 - Overall comfort (0-10 scale)

- Overall dryness (0-10 scale)
 - Ease of insertion (0-10 scale)
 - Ease of removal (0-10 scale)
 - Overall visual quality/clarity (0-10 scale)
 - Overall visual stability (0-10 scale)
 - Overall satisfaction (0-10 scale)
 - Comments by participants
- Monocular and binocular logMAR visual acuity will be recorded with high contrast letters under high and low room illumination.
 - Lens surface and fit will then be assessed and graded according to the CVI grading scales for the following:
 - Lens wettability (0-4 scale)
 - Centration (mm)
 - Post-blink movement (mm)
 - Toric mark visibility
 - Lens orientation (3 measurements per lens)
 - Overall stability of toric mark position
 - Overall lens fit acceptance (0-4 scale)
 - The lenses will be removed and retained. The disposal procedures are detailed in Section 4.7.6.
 - Slit lamp biomicroscopy will be assessed according to the CVI approved study biomicroscopy CRF.
 - There will be a 10 minute wash-out before insertion of lens pair #2.
 - Lens pair #2 will be provided to participants in a manner which does not unmask the participant, as described in Section 4.7.4.
 - The lenses will be inserted by the participant.
 - Procedures of fit and assessment will be repeated as detailed in the dispensing visit, section 4.8.3.
 - The participant will be discharged and reminded to return for the 1-week visit of lens pair #2 and to bring back all lens package foils.

4.8.5 1-WEEK FOLLOW-UP OF PAIR #2 & DISPENSING PAIR #3

Participants will be asked to wear lenses for at least 4 hours prior to the visit appointment. Participants who attend without lenses in-situ (wearing lenses) for at least four hours will be rescheduled.

- The participant will be asked to score their subjective responses by reflecting on a typical day during the previous week of lens wear, as detailed in the subjective ratings form (Appendix 11) and includes the following:
 - Wear time at this visit (hours)
 - Wear time per day during previous 1 week (hours)
 - Comfortable wear time per day during previous 1 week (hours)
 - Overall comfort (0-10 scale)
 - Overall dryness (0-10 scale)
 - Ease of insertion (0-10 scale)
 - Ease of removal (0-10 scale)
 - Overall visual quality/clarity (0-10 scale)
 - Overall visual stability (0-10 scale)
 - Overall satisfaction (0-10 scale)
 - Comments by participants
- Monocular and binocular logMAR visual acuity will be recorded with high contrast letters under high and low room illumination.
- Lens surface and fit will then be assessed and graded according to the CVI grading scales for the following:
 - Lens wettability (0-4 scale)
 - Centration (mm)
 - Post-blink movement (mm)
 - Toric mark visibility
 - Lens orientation (3 measurements per lens)
 - Overall stability of toric mark position

- Overall lens fit acceptance (0-4 scale)
- The lenses will be removed and retained. The disposal procedures are detailed in Section 4.7.6.
- Slit lamp biomicroscopy will be assessed according to the CVI approved study biomicroscopy CRF.
- There will be a 10 minute wash-out before insertion of lens pair #3.
- Lens pair #3 will be provided to participants in a manner which does not unmask the participant, as described in Section 4.7.4.
- The lenses will be inserted by the participant.
- Procedures of fit and assessment will be repeated as detailed in the baseline and dispensing visit, section 4.8.3.
- The participant will be discharged and reminded to return for the 1-week visit of lens pair #3 and to bring back all lens package foils.

4.8.6 1-WEEK FOLLOW-UP OF PAIR #3 & STUDY EXIT

Participants will be asked to wear lenses for at least 4 hours prior to the visit appointment. Participants who attend without lenses in-situ (wearing lenses) for at least four hours will be rescheduled.

- The participant will be asked to score their subjective responses by reflecting on a typical day during the previous week of lens wear, as detailed in the subjective ratings form (Appendix 11) and includes the following:
 - Wear time at this visit (hours)
 - Wear time per day during previous 1 week (hours)
 - Comfortable wear time per day during previous 1 week (hours)
 - Overall comfort (0-10 scale)
 - Overall dryness (0-10 scale)
 - Ease of insertion (0-10 scale)
 - Ease of removal (0-10 scale)
 - Overall visual quality/clarity (0-10 scale)
 - Overall visual stability (0-10 scale)

- Overall satisfaction (0-10 scale)
- Comments by participants
- Participants will be asked their preference between lens pair #1, lens pair #2, and lens pair #3, for a number of considerations:
 - Overall comfort preference
 - Visual quality preference
 - Vision stability preference
 - Overall handling (lens insertion and removal) preference
 - Overall lens preference
- Monocular and binocular logMAR visual acuity will be recorded with high contrast letters under high and low room illumination.
- Lens surface and fit will then be assessed and graded according to the CVI grading scales for the following:
 - Lens wettability (0-4 scale)
 - Centration (mm)
 - Post-blink movement (mm)
 - Toric mark visibility
 - Lens orientation (3 measurements per lens)
 - Overall stability of toric mark position
 - Overall lens fit acceptance (0-4 scale)
- The lenses will be removed and retained. The disposal procedures are detailed in Section 4.7.6.
- Slit lamp biomicroscopy will be assessed according to the CVI approved study biomicroscopy CRF.
- Exit visual acuity will be performed.
- The study exit form will be completed when a participant exits the study. This will occur either at study completion, or if the participant is discontinued from the study at another time. A study exit form must be completed for all participants who have taken a study ID

number. If in the opinion of the investigator post-study follow-up visits are required, the exit form will be completed after the last follow-up visit.

- The participant will be discharged and will sign the study completion forms and receive remuneration for participating in the study.

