4.8.7 UNSCHEDULED VISITS

An unscheduled visit is defined as an interim visit requested by the participant or investigator due to an unanticipated problem. Data recorded at these visits will be entered into the database. Only relevant and applicable unscheduled visit information will be included in the final report as deemed necessary by the lead investigator.

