8 DISCONTINUATION FROM THE STUDY

Participants discontinued from a study will be reimbursed [REDACTED] [REDACTED] (including the initial screening visit). A participant's study participation may be discontinued at any time if, in the opinion of the sponsor or the investigator it is in the

best interest of the participant. All discontinuations will be fully documented on the appropriate study forms and the Discontinuation Form will be completed. The following is a list of possible reasons for discontinuation from the study:

- Screening failure: Participants will be discontinued if they do not meet the inclusion and exclusion criteria outlined in section 4.6.2.
- Unacceptable performance with products to be used in study: Participants may be discontinued if they are unable to achieve acceptable comfort and /or vision with the study products.
- Positive slit lamp finding: Participants may be temporarily or permanently discontinued from the study depending on the severity of the condition and on the judgement of the investigator.
- Adverse event: If a participant experiences an adverse event during the study they may be discontinued based on the clinical judgement of the investigator.
- Symptoms: If the participant has persistent symptoms they may be discontinued based on the clinical judgement of the investigator.
- Disinterest, relocation or illness: The participant may choose to discontinue due to reasons within or beyond their control.
- Violation of protocol or non-compliance: The participant will be discontinued if they are unable or unwilling to follow the protocol specified visit schedules and/or study procedures.
- Instillation of topical ocular medication: The participant will be discontinued if they elect to use a topical ocular medication during the study unless that topical ocular medication is prescribed for a limited duration (less than two weeks) to treat a transient condition; in this case the participant may remain an active participant (at the discretion of the investigator) after stopping topical ocular medication following resolution of the ocular condition).
- Lost to follow-up: The participant will be discontinued if they cannot be contacted and do not return for a final exit visit, and if the investigator has made a reasonable effort to contact the participant for a final study visit.
- Premature termination of the study by the sponsor, the CCLR or the Office of Research Ethics at the University of Waterloo.

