11.2 STATISTICAL ANALYSIS

All data will be analyzed by the CCLR at the University of Waterloo. Summary statistics will be produced (e.g. mean, standard deviation). Data analysis will be conducted using Statistica and / or SPSS. Descriptive statistics will be provided on information regarding baseline variables (age, gender, refractive error distribution, etc.). Analysis of variables will be conducted separately on each eye, and data will not be pooled. A Binomial test will be used to analyze the results for the count data of subjective preferences. The number of “no preference” will be evenly distributed to the two options on the basis they would be equally likely to choose either.

Table 5 lists the primary outcome variables and anticipated statistical procedures.

Table 5: Outcome variables and anticipated statistical procedures

Variable	Analysis	Statistical test
Analogue scales/Numeric scales/Preference scales/VA Lens parameters, Biomicroscopy (continuous variables)	Effect of lens type	RMANOVA/MANOVA/ Friedman /Wilcoxon matched pairs test Tukey HSD post hocs Paired t-test Chi-square test
Biomicroscopy (ordinal variables)	Effect of lens type	Friedman Wilcoxon matched pairs test
Analogue scales/Numeric scales/Lens parameters, Biomicroscopy (continuous)	Relationship between slit lamp findings and analogue scales	Pearson correlation - r
Biomicroscopy (ordinal variables)	Relationship between slit lamp findings and analogue scales	Spearman correlation - rho

The critical alpha level for statistical significance will be set at $p \leq 0.05$, with no adjustments for multiple comparisons.

All participants who were evaluated will be used in the analysis. In the event of missing data, individual data points will be excluded in the analysis and not extrapolated from the collected data.

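### The week-1 overall ratings and Visit 4 preferences are collected only when the lenses are being worn, so a lens stopped for discomfort or poor vision drops out of those comparisons

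*Combined protocol and SAP*

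**What the plan says.** Section 4.8 sets a wear condition for every follow-up visit: "A scheduled follow-up visit may only take place when the participant attends wearing the study lenses". It then deals with those who arrive without lenses: "If this is not the case and the participant is not experiencing any problems with the lenses, the appointment will be rescheduled". Sections 4.8.4 to 4.8.6 add a minimum wearing time and do not repeat the exception for lens problems: "Participants who attend without lenses in-situ (wearing lenses) for at least four hours will be rescheduled".

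The overall comfort, dryness and visual quality ratings are listed inside those visits and are retrospective: "The participant will be asked to score their subjective responses by reflecting on a typical day during the previous week of lens wear". The preference questions appear once, in 4.8.6: "Participants will be asked their preference between lens pair #1, lens pair #2, and lens pair #3, for a number of considerations".

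For a participant in difficulty with a lens there are two other routes. Section 4.8.7 covers unscheduled visits. It enters their data in the database but lists no ratings, and adds: "Only relevant and applicable unscheduled visit information will be included in the final report as deemed necessary by the lead investigator". Section 8 allows withdrawal: "Participants may be discontinued if they are unable to achieve acceptable comfort and /or vision with the study products". Neither section mentions the overall ratings or the preferences.

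On analysis, 11.2 uses all evaluated participants and states: "In the event of missing data, individual data points will be excluded in the analysis and not extrapolated from the collected data". It plans no sensitivity analysis.

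**The concern.** Section 2 names comfort, dryness and visual quality, as ratings and preferences, as the primary outcomes. A wear condition makes sense for visual acuity, lens surface and fit, which cannot be measured without the lens. The overall ratings and the preferences share that condition only because they are listed in the same visit.

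The participants most likely to be missing are those who could not tolerate a lens. They would probably have rated it low and not preferred it, so the missingness is related to the outcome. Leaving those values out makes the failed lens look better than it was. The hypothesis in section 3 is that MD-T performs as well as or better than the two controls. If failures fall mainly on MD-T, the comparison is too favourable to it. If they fall mainly on a control, a real MD-T advantage is understated.

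**Working it through.** **1. What is lost and what survives when a pair is stopped**

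| Item | Where listed | Needs a lens on the eye? | If the pair is stopped |
|---|---|---|---|
| Overall comfort, dryness, visual quality | 4.8.4 to 4.8.6 | No | No text collects it |
| Preferences | 4.8.6 only | No | No text collects them without Visit 4 |
| Acuity, surface, fit | Dispensing and follow-up visits | Yes | Follow-up value rightly missing |
| Comfort at insertion, visual quality at dispensing | 4.8.3, repeated for pairs #2 and #3 | Yes | Already collected |
| Take-home comfort, dryness, visual quality (days 1, 3, 6) | 4.8.3 | Yes | Kept for days worn |

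If the participant is discontinued under section 8, failure on pair #1, #2 or #3 leaves week-1 overall ratings for 0, 1 or 2 lenses and no preference. For the overall ratings, the failed lens is then the one without a value.

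**2. The plan's own figure**

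Inputs from 11.1: difference 5, SD 12.6 (100-point scale), paired t-test, two-sided alpha 0.05, power 80%. The standardized difference is 5/12.6 = 0.397. With n = 52 the noncentrality is 0.397 × √52 = 2.86, and the noncentral t distribution gives power 80.2%. The smallest n reaching 80% is 52, as Table 4 states; at alpha 0.10 it is 41, also as stated. (The effect size of 0.28 printed in 11.1 does not equal 5/12.6 and is not used here.)

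**3. Illustration of selective loss**

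Assumption: k participants have no overall rating for one lens. The documents give no failure rate. Section 4.6.1 allows 52 − 45 = 7 losses from all causes, so k lies between 0 and 7 and is probably small.

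Let G be the mean true difference (other lens minus failed lens) among those lost. The expected observed difference is (52 × 5 − k × G)/(52 − k).

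Suppose those lost are random members of the half with the larger differences. For a normal distribution G is about 5 + 12.6 × √(2/π) = 5 + 12.6 × 0.798 = 15.05.

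- k = 1: (260 − 15.05)/51 = 4.80
- k = 3: (260 − 45.15)/49 = 4.38

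Simulating 200,000 trials and removing k at random from the upper 26 of 52 gives nearly the same means, and the power:

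| k | Mean, selective loss | Power, selective loss | Mean, random loss | Power, random loss |
|---|---|---|---|---|
| 1 | 4.82 | 76.5% | 5.0 | 79.4% (n = 51) |
| 3 | 4.40 | 67.4% | 5.0 | 77.7% (n = 49) |

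At k = 3 the smaller sample costs 80.2 − 77.7 = 2.5 points of power. Selection costs a further 77.7 − 67.4 = 10.3 points.

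**4. The other direction**

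If the true difference is 0 and the k failures are on MD-T, the same formula gives a spurious MD-T advantage of about k × 10.05/(52 − k): 10.05/51 = 0.20 at k = 1 and 30.15/49 = 0.62 at k = 3. Simulation gives 0.19 and 0.60, with a two-sided false-positive rate of about 6% at k = 3.

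**5. Balanced failures**

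Take 7 losses: 2 failing on each of the two compared lenses, drawn from opposite halves, plus 3 at random. The expected difference stays at 5.0 and power is about 75%, close to the 74.0% for 45 participants with random loss.

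**6. Preferences**

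Treat the preference as a two-way choice and start at the significance threshold, where the effect is largest. An exact binomial test of 34 of 52 gives p = 0.036. Losing one of the 34 gives 33 of 51, p = 0.049, still significant. Losing two gives 32 of 50, p = 0.065.

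**The case against.** The strongest reply is that this is ordinary dropout. The four-hour rule only reschedules, ideally within the visit window, and anyone who manages four hours of wear is rated, however uncomfortable the lens. The loss comes from not collecting the items when a pair is stopped, combined with excluding missing points. That is right, and a reader should not infer that the four-hour sentence alone removes the data.

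A reader might also infer that a failed lens enters no paired comparison at all. The documents do not support that. Comfort at insertion and visual quality are rated at every dispensing, and take-home ratings exist for days worn, so a lens that fails as pair #2 or #3 can be compared with earlier pairs on those. They do not fill the whole gap: dryness is not rated at dispensing, neither source contains a preference question, and later take-home entries presuppose continued wear.

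Discontinuation under section 8 is optional, nothing forbids completing the ratings at an unscheduled visit, and every participant with a study ID needs an exit form. This stands as far as it goes. The plan permits collection but does not require it, and Appendices 11, 13 and 27 are not available to show whether the forms do more.

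Finally, participants are adapted wearers who have been trial-fitted with all three lenses, so failures may be few, and balanced failures largely cancel. This stands and limits the size of the point.

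**Conclusion.** The concern holds for the week-1 overall ratings and the Visit 4 preferences. As written, the plan does not collect them from a participant who stops a pair for discomfort or poor vision, and the analysis then omits that lens for a reason related to the outcome.

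The size is uncertain. If 1 to 3 participants are lost on one lens from the half with larger differences, an expected difference of 5 becomes 4.8 to 4.4 and power falls to about 77% to 67%, against 79% to 78% for random loss. This rests on an assumed number of failures, on their falling mainly on one lens, and on the plan's SD. With no failures, or balanced ones, there is little or no bias.

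A reader could push the calculation further. If all 7 allowed losses fell on one lens and were the 7 largest differences, the expected difference would be 1.9 and power 27%. That is an extreme bound: the 7 cover every cause of loss, including relocation and illness, and nothing in the documents suggests such a concentration. Nor does the gap between 4.8 and 4.8.4 to 4.8.6 support a claim of harm to participants; it needs only a wording clarification.

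The change is worth making because it is cheap and because ratings that were never collected cannot be recovered.

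**What to change.** - **4.8.4 to 4.8.6:** keep the four-hour rule, but for visual acuity, surface and fit only.
- **4.8.4 to 4.8.7 and section 8:** state that a participant who stops a pair because of a lens problem completes the Appendix 11 overall ratings for that pair at the unscheduled or exit visit, whether or not lenses are worn. If at least two pairs were dispensed, the participant also answers the preference questions for the pairs tried.
- **11.2:** include these ratings in the analysis, report by lens the number who stopped for discomfort or poor vision, and add one sensitivity analysis that gives a stopped lens the worst rank and counts it as not preferred.
- **Optional:** let a participant who cannot resume one pair go on to the next, at the investigator's discretion.

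The cost is wording, a few extra ratings on existing questionnaires, and ORE approval before implementation (12.3). No extra participants are needed. Some ratings will rest on short wear and must be flagged. Preferences given after two pairs are not the three-way question of Visit 4 and should be used only in the sensitivity analysis.
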